7.10 STATISTICAL ANALYSIS

7.4.1 Analysis Sets

In the efficacy analysis, the **Per Protocol Set (PPS)** will be used as the primary analysis set, while the **Full Analysis Set (FAS)** will serve as the secondary analysis set. For safety analysis, the **Safety Analysis Set** will be used. The definitions are as follows:

- **Per Protocol Set (PPS):**
The PPS includes participants who do not have any major protocol violations (such as not meeting inclusion/exclusion criteria or poor compliance), and who have completed the required assessments of the primary endpoint as specified in the protocol.
- **Full Analysis Set (FAS):**
The FAS includes all participants who received at least one dose of the study drug and had at least one post-baseline assessment for efficacy endpoints. This set reflects the intention-to-treat principle.
- **Safety Analysis Set:**
The Safety Analysis Set includes all participants who received at least one dose of the study drug and had at least one post-baseline safety assessment. All safety data, including adverse events and rescue medication use, will be analyzed in this set.

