6.4 Withdrawal Criteria

- Any clinical adverse event, serious illness, or other medical condition identified by the investigator or treating doctor that suggests continued participation is not in the subject's best interest.
- A voluntary decision by the patient to withdraw from the study.
- If the subject was found to have entered the study in violation of the protocol or if the patient was uncooperative during the study.
- Any subject who required the use of an unacceptable concomitant medication—defined as a medication that interfered with the study—will be addressed with justification from the investigator.

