6.10 Rescue Medication

Rescue medication can be given to patient who have given informed consent. The rescue medication given is only if the subject can not bear the pain and to help reduce pain and per investigator advise. The rescue medication is a drug specifically provided for this study. The use of rescue medication will be recorded. The dosage of rescue medication will be determined by the Investigator.

- Active Ingredients : Paracetamol 600 mg
- Brand name : Sumagesic
- Dose : 1 tablets maximum 3 dose per 24 hours or refer to Investigator advise.
- Method of administration: Oral.

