7.8 CRITERIA AND PROCEDURE FOR DISCONTINUATION FOR PARTICIPANTS

7.8.1 Discontinuation Criteria

Investigator discontinues the study when a subject meets the following criteria.

1. When continuation of the study is difficult due to worsening of the target disease of this study or symptoms caused by the target disease
2. When a significant or persisting noncompliance with the protocol that makes it difficult to ensure safety or influences efficacy assessment was detected

3. When a subject is found not to meet the inclusion criteria for participants of this study or to meet the exclusion criteria
4. When it is difficult to continue the study or a subject requests for discontinuation due to onset of AEs
5. When a subject requests for discontinuation (not in relation to AEs)
6. When a subject stops visiting the site, making it difficult to continue the study
7. Other cases in which Investigator considers it difficult to continue the study

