
Missing Data Handling

- **Primary Analysis** will be based on the **Per Protocol Set**, with sensitivity analysis using **Full Analysis Set (FAS)** under **intention-to-treat (ITT)** principles.
- **Multiple imputation** will be considered for missing primary endpoint data if the proportion of missing data exceeds 5%.

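### Equivalence is decided on the Per Protocol Set with no requirement that the Full Analysis Set agree, so participants who stop early for worsening can fall outside the deciding analysis

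*Protocol*

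**What the plan says.** Section 7.4.1 fixes the hierarchy: "In the efficacy analysis, the Per Protocol Set (PPS) will be used as the primary analysis set", with the FAS second. Missing Data Handling in 7.4.2 repeats it: "Primary Analysis will be based on the Per Protocol Set, with sensitivity analysis using Full Analysis Set (FAS) under intention-to-treat (ITT) principles". The pairwise two one-sided tests (TOST) of mean BPI change against ±1.0, also in 7.4.2, are therefore decided on the PPS.

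PPS members must have no major violation, illustrated by "such as not meeting inclusion/exclusion criteria or poor compliance", and must be participants "who have completed the required assessments of the primary endpoint as specified in the protocol". Section 7.9.1 schedules the primary assessment (Form 2) at Visits 1, 2 and 3, and 7.7.2 counts a participant as complete only after the Visit 3 examination.

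Two routes out of the trial bear on this. The first discontinuation criterion in 7.8.1 is "When continuation of the study is difficult due to worsening of the target disease". Section 6.4 lists as a withdrawal criterion "Any subject who required the use of an unacceptable concomitant medication", subject to the investigator's justification; 6.14 names opioids and oral NSAIDs among such medications. Section 7.8.2 asks for the scheduled observations to be made when a participant discontinues.

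For missing data, multiple imputation "will be considered for missing primary endpoint data if the proportion of missing data exceeds 5" per cent.

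**The concern.** In an equivalence trial a smaller observed difference helps the claim. Participants who stop because their pain worsens, or who need an opioid or an oral NSAID, are likely to be treatment failures rather than random losses. If they leave the deciding analysis, and more of them come from one arm, the comparison of those who remain no longer reflects the randomised comparison.

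The FAS would show this, but as written it has no vote. The trial could report equivalence on the PPS while the FAS interval crosses the margin, and the protocol's hierarchy would support that report. This is not a detail left to a later analysis plan, because the protocol itself states which set decides.

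**Working it through.** **Who leaves the PPS.** No single rule says that failures are excluded. It follows from reading sections together:

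1. 7.4.1 requires completed primary-endpoint assessments.
2. 7.9.1 and 7.7.2 place the last of these at Visit 3.
3. 7.8.1 (worsening) and 6.4 (unacceptable medication) allow a participant to leave before Visit 3.
4. Someone who does so lacks the Visit 3 assessment and does not meet the PPS definition.

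Imputation cannot bring these participants back into the primary analysis, because PPS members have the endpoint by definition. It can act only in the FAS.

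**Size of the possible distortion.** The protocol gives no failure rates, so there is no figure of its own to reproduce. From the protocol: margin 1.0 (6.7, 7.4.2), SD 1.81, 60 per arm and adjusted alpha 0.0167 (6.7). Assumed: the failure rates, and the gap g by which failures improve less than completers in their own arm.

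Let f be the proportion failing, and let D be the control improvement minus the test improvement. Then

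D(all treated) = D(PPS) + (f_test − f_control) × g

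| f test | f control | g | Shift |
|---|---|---|---|
| 10% | 10% | 3 | 0 |
| 10% | 2% | 3 | 0.08 × 3 = 0.24 |
| 15% | 5% | 3 | 0.10 × 3 = 0.30 |
| 20% | 5% | 4 | 0.15 × 4 = 0.60 |

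In the second row, a completers' difference of 0.76 would correspond to 0.76 + 0.24 = 1.00 among all treated, exactly at the margin. The sign matters: if failures are commoner in the arm whose completers do better, excluding them enlarges the PPS difference instead.

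**Effect on the decision.** TOST was simulated for one pair of arms, 60 per arm, SD 1.81, 6,000 runs per scenario, comparing an analysis that excludes failures with one that keeps everyone. The figures are the chance of declaring equivalence.

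| f test / control, g | D(PPS) | D(all) | 0.05: excluded / kept | 0.0167: excluded / kept |
|---|---|---|---|---|
| 15% / 5%, 3 | 0.7 | 1.0 | 22% / 5% | 9% / 2% |
| 15% / 5%, 3 | 0 | 0.3 | 78% / 57% | 52% / 31% |
| 10% / 10%, 3 | 0 | 0 | 78% / 71% | 53% / 43% |

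The first row shows the risk: the difference among all treated is at the margin, yet the completers' analysis declares equivalence far more often than the nominal rate. The last row shows that balanced failure brings no bias; the lower figure with everyone kept reflects added variance.

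**The case against.** A per-protocol analysis is a legitimate part of an equivalence trial, since a full-set analysis that keeps non-compliers can itself blur differences. The protocol plans both sets. All three arms are active topical NSAIDs used for about six days, and nothing in the documents predicts unequal failure. All of this stands. What it does not answer is why the FAS has no say in the conclusion.

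Several stronger readings are tempting but unsupported:

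- **Excluding failures necessarily favours equivalence.** It does so only if failure rates differ between arms in the matching direction.
- **Use of prohibited medication always removes a participant.** It is not named among the major violations, and 6.4 leaves such cases to investigator justification. Exclusion is certain only if the participant is withdrawn before Visit 3.
- **Nothing is recorded for those who stop.** Section 7.8.2 asks for the assessments at discontinuation, so a last BPI score may exist. It can feed the FAS, though it does not complete the Visit 3 assessment.
- **The imputation rule contradicts the PPS.** It fits naturally with the FAS analysis named just before it. Its weakness is that it is only to be considered.
- **Rescue paracetamol is part of the same defect.** Section 6.10 does say "The dosage of rescue medication will be determined by the Investigator", but tablets supplied to all are for use only when pain is unbearable. Users of permitted rescue are not excluded from the PPS for that reason, and 7.4.2 compares rescue use between arms by count regression. Who can see the allocation is likewise a separate question.
- **The 10% dropout allowance supports a 10% failure rate.** That allowance is all-cause and trial-wide.

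**Conclusion.** The point holds in a limited form. The protocol lets the PPS alone decide equivalence, and participants who stop before Visit 3 for worsening, or who are withdrawn before then for unacceptable medication, are outside that set. An equivalence claim could therefore rest on the PPS when the FAS does not support it.

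Whether this would bias the result is unknown. The bias is zero with balanced failures and 0.24 points, about a quarter of the margin, under the assumed 10% against 2% with a 3-point gap. Larger figures need larger assumed imbalances. The exclusion itself is the natural reading of several sections together, not an explicit rule. This should be corrected before database lock, but it does not show that the trial's conclusion would be wrong.

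**What to change.** In 7.4.1 and in Missing Data Handling, make three changes:

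1. State that equivalence for a pair is concluded only if the confidence interval for the difference in mean BPI change lies within ±1.0 in both the PPS and the FAS.
2. Analyse the FAS with all available Visit 2, Visit 3 and discontinuation-visit BPI scores by one prespecified method, such as a mixed model, in place of imputation that is only to be considered.
3. Add a supportive FAS analysis that counts discontinuation for worsening as no improvement. It is needed because a mixed model usually assumes data missing at random, which does not address informative stopping. Keep it supportive: giving a fraction f of each arm zero change turns a difference d into (1 − f)d, which also shrinks differences. For the same reason, do not extend it to users of permitted rescue.

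The data are already scheduled for collection, so the change is wording. The cost is some power. In the balanced scenario above, with 10% failing in each arm and a 3-point gap, the chance of meeting the criterion in both sets cannot exceed the lower of the two figures: 71% instead of 78% at 0.05, and 43% instead of 53% at 0.0167. That scenario treats a full 10% as failures; with fewer, the loss is smaller.

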4. STUDY OBJECTIVES

The objectives of this study is to demonstrate the equivalency of efficacy and safety in reducing musculoskeletal pain between Piroxicam plus Counterirritant gel versus Piroxicam gel and Diclofenac gel, applied for 6 ± 1 days in Indonesian population.

Justification:

Piroxicam plus Counterirritant, Piroxicam, Diclofenac are considered as topical Non-Steroid Anti Inflammatory Drugs (NSAIDs). Diclofenac more common to use as a standard topical treatment since they have more clinical studies data than others topical NSAIDs. To demonstrate that Piroxicam plus Counterirritant has the same efficacy with Piroxicam, Diclofenac, the dedicated clinical study need to be conducted.

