The selection of difference more than equal to 3 was chosen because if the participant has moderate pain at the beginning of the treatment, then at the end of the treatment there is a decrease in pain to mild pain. This can be seen that the treatment is effective in dealing with musculoskeletal pain.

5.2 Secondary End-Point:

- 1) In data related to safety assessment, the number of participants who experienced adverse events (including serious adverse events) with each symptom present will be recorded and causality of adverse events and serious adverse events assessed with the help of Naranjo's algorithm

Justification:

At the 1st visit, participants will bring home Participant's Diary. Participants need to fill in if they experienced with others symptoms after get the treatment. Also they need to file the rescue medication that they consume during the study timeline. On the 2nd visit and last visit the Investigator will ask about the diary and confirmed the symptoms and medication. When there is safety report, the Investigator will fill in the Safety Form from BPOM RI (Form Kuning MESO) and assess the safety events with the help of Naranjo's algorithm.

The type of symptoms and the number of participants who have symptoms and including side effects will be recorded and become data related to product safety.

- 2) Investigator Assessment on Participants motions, through Range of Motion (ROM) and Muscle test.

Justification:

One of the symptoms that must be assessed when there is musculoskeletal pain is the range of motion and muscle movement to perform an activity. Therefore, an assessment for the examination of the range of motion and muscle strength carried out by the examining doctor is needed to determine the effect of the treatment carried out in the success of performing the activity.

The effectiveness of the treatment will be seen from the progress in the range of motion that can be performed by the participant at the end of the treatment compared to the beginning of the treatment according to scientific standards.

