7.7.2 Study period and process

The study period for each participant is defined as “the period from the day of consent to the end of study (the day on which final tests and observation are finished or the day of discontinuation of the study).

The participants considered as a complete visit after the 3rd visit examination on 6 ± 1 days visit.

[figure not shown]
- 1st visit consider as Day 0
- 2nd visit is on Day 3 ± 1 days
- 3rd visit is on Day 6 ± 1 days

The study's flow in Day 0 :

- 1) The registration officers will receive participants who register at the Eminence clinic and ask about symptoms related to the participant's visit. If the Participant complains of pain, the patient will be asked to fill out a registration form.
- 2) The Principal Investigator or Sub Investigator will ask some questions (anamnesis) about the symptoms and explain about a clinical study that is conducted in the clinic. The PI or Sub-I will ask the Participant's willingness to join the research and explain regarding informed consent. If the Participant agrees, an informed consent will be signed.
- 3) The participants are asked to complete the Individual Assesment of Pain.
 - a. Form 2 : Pemeriksaan Inventerisasi Rasa Nyeri Singkat
- 4) The examination was carried out by conducting anamnesis, physical examination to confirmation the musculoskeletal pain, range of motion and muscle test and confirmation related to the inclusion and exclusion criteria. If needed a radiologic examination will be conducted.
- 5) In the examination, the PI or Sub-I should complete some Forms :
 - a. Form 3 : Pemeriksaan Awal Rasa Nyeri
 - b. Form 4 : Pemeriksaan Indikator Rasa Nyeri Non Verbal
 - c. Form 5 : Pemeriksaan Rentang Gerak
 - d. Form 6 : Pemeriksaan Kekuatan Otot
- 6) The PI or Sub-I will provide a diagnosis and therapy appropriate to the diagnosis.

- 7) Randomization of participants is carried out helped by Study Coordinator. The administration of therapeutic drugs according to the randomization list by a physiotherapist. The physiotherapist will provide information related to how to apply topical drugs to participants and provide the first dose of the investigational product in the therapy room.
 - a. Form 7: Pemberian aplikasi obat topikal by Physiotherapist
 - b. Form 8: Sensasi Termal by Participant
- 8) Each participant will get physical therapy program referred to standard protocol and diagnosis

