7.8.2 Discontinuation Procedures

When any event corresponding to “Discontinuation Criteria” occurs during the study treatment, Investigator discontinues the administration of study drugs, performs the observation and tests specified in “ Schedule and Efficacy and Safety Endpoints,” and enter the results, discontinuation day, and reason for discontinuation in case report form.

Appropriate treatment including alternative therapies is provided after discontinuation.

When the study is discontinued due to occurrence of a safety problem in the subject concerned, appropriate measures are taken and the problem is addressed in accordance with “ Ensuring Safety of Participants.”

When a subject stops visiting the site, Investigator asks a subject to visit the site and efforts are made to perform the observation and tests specified in “Schedule, Efficacy and Safety Endpoints.”

If the designated observation and tests cannot be performed, Investigator promptly conducts follow-up investigation on the course after the latest observation and AEs over the phone, by letter, or other possible methods and enters the result in case report form. When confirmation was made with a person other than the subject for a compelling reason, the reason and the relationship of this person with the subject are entered in case report form.

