7.4.2 Statistical Analysis Plan

The statistical analysis will be performed after data finalization and database lock, following the predefined analysis sets (PPS, FAS, and Safety Analysis Set). All analyses will be conducted using standard statistical software (e.g., SPSS, SAS, or R), with the level of statistical significance set at $p < 0.05$, unless otherwise adjusted.

Efficacy Analysis

- **Primary Endpoint (Pain Score using Brief Pain Inventory):**
 - **Test: Analysis of Covariance (ANCOVA)** adjusting for baseline BPI score

- **Equivalence testing:** Pairwise comparisons using **two one-sided t-tests (TOST)** to assess whether the difference in mean change from baseline falls within the equivalence margin (± 1.0)
- **Assumptions:** Normality and homogeneity of variance will be checked. If violated, non-parametric equivalent (e.g., **Wilcoxon rank-sum test**) will be used.
- **Secondary Endpoints:**
 - **Range of Motion (ROM) and Muscle Strength:**
 - **Test:** Repeated Measures ANOVA or mixed-effects model, depending on data completeness and correlation structure
 - If non-normal: **Friedman test** or **Wilcoxon signed-rank test** for within-group, **Kruskal-Wallis test** for between-group comparisons.
 - **Thermal Sensation, Comfort, and Acceptance (ASHRAE Scale):**
 - **Test:** Chi-square test or Fisher's exact test for categorical comparisons
 - **Ordinal regression** may be used to explore patterns of thermal perception across groups.
 - **Responding Analysis (pain reduction ≥ 3 points):**
 - **Test:** Chi-square test for group-wise comparison of response rates
 - **Risk difference** and **number needed to treat (NNT)** will be calculated.

Safety Analysis

- **Adverse Events (AEs) and Adverse Drug Reactions (ADRs):**
 - **Test:** Chi-square test or Fisher's exact test for comparing incidence across groups
 - Descriptive statistics for type, severity, onset, and duration
 - **Severity grading** and **causality assessment** using **Naranjo's algorithm**.
- **Rescue Medication Use:**
 - **Test:** Poisson regression or negative binomial regression if data are overdispersed
 - Summarized as a mean number of doses used per participant and compared between groups.

Demographic and Baseline Characteristics

- **Continuous Variables** (e.g., age, BMI):
 - **Test:** One-way ANOVA or **Kruskal-Wallis test** (if non-normal distribution)
- **Categorical Variables** (e.g., sex, diagnosis):
 - **Test:** Chi-square test or Fisher's exact test as appropriate

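### The Safety Analysis Set requires a post-baseline safety assessment as well as a dose, so membership depends on later contact and a recorded Day 0 reaction could be left out

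*Protocol*

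**What the plan says.** Section 7.4.1 sets two conditions for the Safety Analysis Set. It takes participants who "received at least one dose of the study drug and had at least one post-baseline safety assessment". It then adds: "All safety data, including adverse events and rescue medication use, will be analyzed in this set". The protocol defines no wider all-dosed set, and it does not say what counts as a post-baseline safety assessment.

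The set feeds analyses that matter to the trial:
- Section 4 states the objective as to "demonstrate the equivalency of efficacy and safety in reducing musculoskeletal pain".
- Section 5.2 makes AEs the first secondary endpoint: "the number of participants who experienced adverse events (including serious adverse events) with each symptom present will be recorded".
- Section 7.4.2 compares AEs by a chi-square test or Fisher's "exact test for comparing incidence across groups".

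On timing, section 7.7.2 has the physiotherapist "provide the first dose of the investigational product in the therapy room" on Day 0, the same visit at which baseline pain, motion and strength are assessed. The next visit follows some days later: "2nd visit is on Day 3 ± 1 days".

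The protocol also provides for contact after dosing. The schedule in section 7.9 marks AE recording on Day 0, and section 7.9.2 has participants record AE symptoms from Day 0. Section 7.7.2 gives daily reminders by the study coordinator. Where visit tests cannot be done, section 7.8.2 says the "Investigator promptly conducts follow-up investigation on the course after the latest observation and AEs over the phone", by letter or by other means.

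**The concern.** A safety population normally consists of everyone exposed. Here a second condition is added that depends on what happens after exposure. Everyone who starts treatment is dosed on site on Day 0, and two to four days then pass before the next scheduled visit. A participant who leaves in that interval and cannot be reached may be removed from the AE tables, although exposed.

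The sharper problem is the word post-baseline. Day 0 contains both the baseline assessments and the first application. Nothing says whether an observation made on Day 0 after the application is post-baseline. Two analysts could therefore build different safety sets from the same data, and one of those sets could omit an application-site reaction that is already on record. In a trial that aims to show similar safety and tests AE incidence between arms, who is in the denominator should not turn on an undefined term.

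**Working it through.** **Inputs from the protocol.** Section 6.7 gives 54 per group, 162 in total, 10% dropout, 180 recruited and 60 per arm. Section 7.7.2 puts the first dose on Day 0 and the second visit at Day 3 ± 1. The protocol gives no AE rate and no figure for loss before the second visit, so every event count and exclusion count below is an assumption.

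**1. The plan's own figure.** 162 / (1 − 0.10) = 180, and 180 / 3 = 60 per arm, as stated. Ten per cent of 60 is 6. That is dropout over the whole trial. Anyone who leaves after the second visit already has a later assessment, so 6 per arm is an extreme ceiling for this exclusion, not an expected number.

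**2. Two readings of the condition.** Take a participant dosed on Day 0, with a reaction recorded in the therapy room, and never reached again.
- Read by time of dose: the record was made after the first application, so the participant is in the set and the event counts.
- Read by visit: Day 0 is the baseline visit and nothing later exists, so the participant and the recorded event are both out.

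**3. Effect on the reported rate in one arm of 60.** The reported rate is recorded events among those kept, divided by (60 − excluded). The all-dosed rate is all recorded events divided by 60.

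| Assumed case | Current set | All-dosed set |
|---|---|---|
| A1. 6 recorded events; 1 person without a recorded event excluded | 6/59 = 10.2% | 6/60 = 10.0% |
| A2. 6 recorded events; 6 people without a recorded event excluded (ceiling) | 6/54 = 11.1% | 6/60 = 10.0% |
| B. 6 recorded events, 2 of them on Day 0 in people then excluded | 4/58 = 6.9% | 6/60 = 10.0% |
| C. 6 true reactions, 2 never reported by people then excluded | 4/58 = 6.9% | 4/60 = 6.7% |

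- Cases A1 and A2: the clause raises the reported rate, by 0.2 points with one exclusion and 1.1 points at the ceiling.
- Case B: the clause lowers it by 10.0 − 6.9 = 3.1 points. This needs the visit-based reading and no later contact.
- Case C: the true rate is 6/60 = 10.0%, and neither definition recovers it. The all-dosed set changes only the denominator, and its 6.7% is slightly further from the truth than 6.9%.

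**The case against.** The strongest reply is that the protocol makes the exclusion rare and points to the benign reading. AEs are scheduled for recording on Day 0, and the participant's own record starts that day, so a reaction noted after the first application is naturally a safety assessment after baseline. Daily reminders give a route to news before the second visit. Section 7.8.2 calls for the scheduled observations when treatment is discontinued. For those who stop attending, it calls for AE follow-up by phone, letter or other means, with information from another person accepted for a compelling reason. Only someone with no contact by any of these routes is at risk of leaving the set, and most such people have no recorded event to lose.

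Most of that stands, and it limits the size of the point. It does not settle it: the protocol never says that these contacts, or Day 0 records after dosing, satisfy the condition. If the follow-up works, the clause is unnecessary. If it fails, the clause removes exposed participants.

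A reader might infer more: that the rule makes the counterirritant gel look better tolerated than it is. The documents do not support this. They give no AE rates and no sign of unequal early departure. The direction also depends on whether a recorded event is lost (case B) or only people without one (cases A1 and A2). Nor should 4/58 against 6/60 be read as the general cost of the clause. That contrast applies only to recorded Day 0 reactions that are then excluded.

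**Conclusion.** The point holds as a defect of definition. Safety membership depends on contact after dosing, and an undefined term leaves open whether a recorded Day 0 reaction can be dropped. The effect is probably small: about one percentage point or less, and upward, when those excluded have no recorded event. It is downward only when a recorded Day 0 event is discarded, 3.1 points in the assumed example of two such events. These sizes rest on assumed counts with 60 per arm. No bias in favour of any arm is shown. Minor; a free improvement.

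**What to change.** In section 7.4.1, define the Safety Analysis Set as all participants who received at least one application of study drug, and delete the post-baseline condition. State that observations made on Day 0 after the first application count as safety data. In the safety tables, report by arm the number of participants with no later safety contact, so that the reader can see how much reporting may be missing, since no set definition can recover reactions nobody reported. The cost is a short wording change, with no effect on sample size, visits or data collection.
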